1. Has **evaluable** disease as defined as lesions that can be accurately measured at least in one dimension by radiographic examination or physical examination or other lesions such as bone lesions, leptomeningeal disease, ascites, pleural/pericardial effusions, lymphangitis cutis/pulmonitis or hepatosplenomegaly from disease.
2. Has one of the following histologically confirmed tumors:
 - Rhabdoid tumor:
 - Atypical teratoid rhabdoid tumor (ATRT) (Closed to enrollment)
 - Malignant rhabdoid tumor (MRT)
 - Rhabdoid tumor of the kidney (RTK)
 - Selected tumors with rhabdoid features

- INI1-negative tumor:
 - Epithelioid sarcoma (ES)
 - Epithelioid malignant peripheral nerve sheath tumor (EMPNST)
 - Extraskkeletal myxoid chondrosarcoma (EMC)
 - Myoepithelial carcinoma
 - Renal medullary carcinoma (RMC)
 - Other INI1-negative malignant tumors (e.g., de-differentiated chordoma) NOTE: Requires prior Sponsor approval
 - Synovial sarcoma with SS18-SSX rearrangement (closed to enrollment)
NOTE: Evidence of diagnostic pathology of original biopsy confirmed by a CLIA/CAP or other Sponsor-approved certified laboratory must be available.
3. **For subjects with ATRT, MRT, RTK, or tumors with rhabdoid features only:** The following test results must be available:
- Morphology and immunophenotypic panel consistent with rhabdoid tumor, and
 - Loss of INI1 or SMARCA4 confirmed by immunohistochemistry (IHC), or
 - Molecular confirmation of tumor bi-allelic INI1 or SMARCA4 loss or mutation when INI1 or SMARCA4 IHC is equivocal or unavailable
4. **For subjects with INI1-negative tumor only:** The following test results must be available:
- Morphology and immunophenotypic panel consistent with INI1-negative tumors, and
 - Loss of INI1 confirmed by IHC, or
 - Molecular confirmation of tumor bi-allelic INI1 loss or mutation when INI1 IHC is equivocal or unavailable
5. **For subjects with synovial sarcoma only:** The following test results must be available:
- Morphology consistent with synovial sarcoma, and
 - Cytogenetics or FISH and/or molecular confirmation (e.g., deoxyribonucleic acid [DNA] sequencing) of SS18 rearrangement t(X;18)(p11;q11)

For Dose Expansion Only:

To be eligible for enrollment in Dose Expansion, a subject must meet ALL of the following criteria in addition to the inclusion criteria for ALL subjects listed above:

1. Has measurable disease as defined in Section 8.5.3.
2. Has one of the following histologically confirmed tumors:

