14.4.2 Analysis of Secondary Efficacy Endpoints

In dose escalation, the ORR will be summarized by dose level and overall.

In addition, the ORR will be summarized by dose level across the dose escalation and dose expansion parts (including cohorts) and overall. For each dose level and cohort with at least 20 subjects and overall across the study, an exact 95% CI for ORR will be calculated.

Progression-Free Survival (PFS) is defined as the interval of time between the date of the first dose of study drug and the earliest date of disease progression or death due to any cause.

For subjects who progressed or died after an extended period without adequate assessment, the time of PFS will be censored at their date of last adequate assessment prior to progression or death even if subsequent information is available regarding progression or death. An adequate

assessment is defined as an assessment where the Investigator determined response is CR, PR, or SD. The date of response at that assessment will be used for censoring. Specific rules for identifying extended loss to follow-up or extended time without an adequate assessment are provided in the SAP.

For subjects who receive subsequent anticancer therapy prior to the date of documented progression or death, the time of PFS will be censored at the last adequate assessment (i.e., last assessment of CR, PR or SD) prior to the initiation of that anticancer therapy.

For other subjects who do not progress or die, the time of PFS will be censored at the date of the last adequate tumor assessment.

Overall Survival (OS) is defined as the interval of time between the date of the first dose of study drug and the date of death due to any cause. For subjects who do not die, the time of death will be censored at the date of last contact. Death due to any cause will be included.

Within each cohort and overall, PFS and OS will be calculated using the Kaplan-Meier method. PFS and OS at 24 and 56 weeks and overall along with the associated 95% CIs will be provided. If there are a sufficient number of PFS events (i.e., progressions or deaths), median PFS, first and third quartiles and 90% CI, will be estimated using the Brookmeyer-Crowley method ([Brookmeyer, 1982](#)). If there are a sufficient number of deaths, median OS, first and third quartiles and 95% CI, will be estimated using the Brookmeyer-Crowley method. Figures and listings of PFS and OS will also be provided.

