 - c. FDG-PET may be used to upgrade a response to a CR in a manner similar to a biopsy in cases where a residual radiographic abnormality is thought to represent fibrosis or scarring. The use of FDG-PET in this circumstance should be prospectively described in the protocol and supported by disease-specific medical literature for the indication. However, it must be acknowledged that both approaches may lead to false positive CR due to limitations of FDG-PET and biopsy resolution/sensitivity.

Note: A ‘positive’ FDG-PET scan lesion means one which is FDG avid with an uptake greater than twice that of the surrounding tissue on the attenuation corrected image.

Disease Evaluation Guidelines

Measurable Disease

Measurable lesions are defined as those that can be accurately measured in at least one dimension (longest diameter to be recorded) as:

- ≥ 20 mm (≥ 2 cm) by chest X-ray
- ≥ 10 mm (≥ 1 cm) with CT scan, MRI, or calipers by clinical exam

Note: Tumor lesions that are situated in a previously irradiated area might or might not be considered measurable.

Malignant lymph nodes (LN) can be considered pathologically enlarged and measurable, a LN must be ≥ 15 mm (≥ 1.5 cm) in short axis when assessed by CT scan (CT scan slice thickness recommended to be no greater than 5 mm [0.5 cm]). At baseline and follow-up, only the short axis will be measured and followed.

Non-Measurable Disease

All other lesions (or sites of disease), including small lesions (longest diameter < 10 mm [< 1 cm] or pathological LN with ≥ 10 to < 15 mm [≥ 1 to < 1.5 cm] short axis), are considered non-measurable disease. Bone lesions, leptomeningeal disease, ascites, pleural/pericardial effusions, lymphangitis cutis/pulmonitis, inflammatory breast disease, and abdominal masses (not followed by CT or MRI), are considered as non-measurable.

Note: Cystic lesions that meet the criteria for radiographically defined simple cysts should not be considered as malignant lesions (neither measurable nor non-measurable) since they are, by definition, simple cysts.

‘Cystic lesions’ thought to represent cystic metastases can be considered as measurable lesions, if they meet the definition of measurability described above. However, if non-cystic lesions are present in the same subject, these are preferred for selection as target lesions.

Target Lesions

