All measurable lesions up to a maximum of two lesions per organ and five lesions in total, representative of all involved organs, should be identified as **target lesions** and recorded and measured at baseline. Target lesions should be selected on the basis of their size (lesions with the longest diameter), be representative of all involved organs, but in addition should be those that lend themselves to reproducible repeated measurements. It may be the case that, on occasion, the largest lesion does not lend itself to reproducible measurement in which circumstance the next

largest lesion which can be measured reproducibly should be selected. A sum of the diameters (longest for non-nodal lesions, short axis for nodal lesions) for all target lesions will be calculated and reported as the baseline sum diameters. If a LN(s) is to be included in the sum, then only the short axis is added into the sum. The baseline sum diameters will be used as reference to further characterize any objective tumor regression in the measurable dimension of the disease.

Non-Target Lesions

All other lesions (or sites of disease) including any measurable lesions over and above the 5 target lesions should be identified as **non-target lesions** and should also be recorded at baseline. Measurements of these lesions are not required, but the presence, absence, or in rare cases unequivocal progression of each should be noted throughout follow-up.

Response Criteria

Target Lesion Evaluation

Assessment of target lesion(s) response is defined as:

- Complete Response (CR): Disappearance of all target lesions. Any pathological LN must be <10 mm in the short axis.
- Partial Response (PR): At least a 30% decrease in the sum of the diameters of target lesions, taking as a reference, the baseline sum of the diameters (e.g., percent change from baseline).
- Stable Disease (SD): Neither sufficient shrinkage to qualify for PR nor sufficient increase to qualify for progressive disease.
- Progressive Disease (PD): At least a 20% increase in the sum of the diameters of target lesions, taking as a reference, the smallest sum of diameters recorded since the treatment started (e.g., percent change from nadir, where nadir is defined as the smallest sum of diameters recorded since treatment start). In addition, the sum must have an absolute increase from nadir of 5 mm.
- Not Applicable (NA): No target lesions at baseline.

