Note: Subjects with a global deterioration of health status requiring discontinuation of treatment without objective evidence of disease progression at that time should be reported as “*symptomatic deterioration*.” Every effort should be made to document the objective progression even after discontinuation of treatment.

Best Overall Response for Subjects with Non-Target Disease

Non-Target Lesions	New Lesions	Overall Response
CR	No	CR
Non-CR/non-PD	No	Non-CR/non-PD*
Not all evaluated	No	Not Evaluated
Unequivocal PD	Yes or No	PD
Any	Yes	PD

Abbreviations: CR, complete response; PD, progressive disease; SD, stable disease

*‘Non-CR/non-PD’ is preferred over ‘stable disease’ for non-target disease since SD is increasingly used as an endpoint for assessment of efficacy in some trials so to assign this category when no lesions can be measured is not advised

Notes:

- Subjects with a global deterioration of health status requiring discontinuation of treatment without objective evidence of disease progression at that time should be classified as having "symptomatic deterioration." Objective response status is determined by evaluations of disease burden. Every effort should be made to document the objective progression even after discontinuation of treatment.
- In some circumstances, it may be difficult to distinguish residual disease from normal tissue. When the evaluation of CR depends on this determination, it is recommended that the residual lesion be investigated (fine needle aspirate/biopsy) to confirm the CR.

Confirmation Criteria

To be assigned a status of PR or CR, a confirmatory disease assessment should be performed no less than 4 weeks (28 days) after the criteria for response are first met.

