APPENDIX 5: RESPONSE ASSESSMENT IN NEURO-ONCOLOGY (RANO)

As discussed in (Wen, 2010).

Measurable disease is defined as bi-dimensionally contrast-enhancing or enhancing lesions with clearly defined margins by magnetic resonance imaging (MRI) scan, with 2 perpendicular diameters of at least 10 mm, visible on two or more axial slices that are preferably, at most, 5 mm apart with 0 mm skip.

Non-measurable disease is defined as either uni-dimensionally measurable lesions, masses with margins not clearly defined, or lesions with maximal perpendicular diameters less than 10 mm.

All measurable and non-measurable lesions must be assessed using the same techniques as at baseline.

Complete response (CR): Requires all of the following:

- complete disappearance of all enhancing measurable and non-measurable disease sustained for at least 4 weeks
- no new lesions
- stable or improved non-enhancing (T2/fluid-attenuated inversion recovery [FLAIR]) lesions
- subjects must be off corticosteroids (or on physiologic replacement doses only)
- stable or improved clinically

Note: Subjects with non-measurable disease only cannot have a CR; the best response possible is SD.

Partial response (PR): Requires all of the following:

- $\geq 50\%$ decrease compared with baseline, in the sum of products of perpendicular diameters of all measurable enhancing lesions sustained for at least 4 weeks
- no progression of non-measurable disease; no new lesions
- stable or improved non-enhancing (T2/FLAIR) lesions on same or lower dose of corticosteroids compared with baseline scan
- corticosteroid dose at the time of the scan evaluation should be no greater than the dose at time of baseline scan
- stable or improved clinically

Note: Subjects with non-measurable disease only cannot have a PR; the best response possible is SD.

Stable disease (SD): Requires all of the following:

- does not qualify for CR, PR, or progression
- stable non-enhancing (T2/FLAIR) lesions on same or lower dose of corticosteroids compared with baseline scan

In the event that the corticosteroid dose was increased for new symptoms and signs without confirmation of disease progression (PD) on neuro-imaging, and subsequent follow-up imaging shows that this increase in corticosteroids was required because of PD, the last scan considered to show SD will be the scan obtained when the corticosteroid dose was equivalent to the baseline dose.

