15.1. OBJECTIVE RESPONSE RATE AND DURATION OF RESPONSE

Best Overall Response (BOR)

The summaries of BOR will include number and percentage of subjects in each of these categories:

- Complete response (CR)

- Partial response (PR)
- Stable disease (SD)
- Progressive disease (PD)
- Not Evaluable (NE)
- Unknown/Missing

Confirmation of CR/PR is required at least 28 days after the initial CR/PR was first met. Subjects will be evaluated for response based on the following disease appropriate criteria:

- For CNS tumors, response will be assessed based on RANO (Wen PY, 2010).
- Solid tumors will be assessed based on RECIST version 1.1 (Eisenhauer EA, 2009).

Objective Response Rate

ORR is defined as the percentage of subjects achieving a confirmed CR or PR from the start of tazemetostat until PD or the start of subsequent anti-cancer therapy, whichever is earlier, according to the appropriate disease evaluation criteria.

Subjects with not evaluable, unknown or missing best response will be handled as non-responders, i.e. they will be included in the denominator when calculating the ORR.

For dose escalation, ORR (secondary endpoint) will be summarized by dose level and overall.

For dose expansion, ORR (primary endpoint) will be summarized by cohort and overall. An exact 95% binomial CI for ORR in each cohort and overall will be provided as well.

In addition, ORR will be summarized by dose level across the dose escalation and dose expansion phases and overall. For each dose level and overall, an exact 95% CI for ORR will be calculated.

Also, a subgroup analysis of ORR by prior radiotherapy (Yes vs No) will be performed for the expansion phase by cohort and overall, and for the entire study by dose level and overall.

A plot of the maximum percent tumor reduction from baseline in target lesions for each subject will be provided.

Duration of Response

DOR will be calculated only for subjects with a confirmed CR or PR. DOR is defined as the interval of time from the first documented evidence of confirmed CR or PR until the first

documented PD or death due to any cause, whichever occurs first.

DOR censoring rules will follow those of the PFS analysis defined in **Table 3** below.

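### Escalation admits children whose disease is not measurable and who cannot have a PR (or any response under RANO), yet they stay in the ORR by dose level pooled with expansion and in the whole-study ORR

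*Protocol*

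**What the plan says.** **Entry.** For escalation, the protocol (Synopsis and Section 4.2.1, item 1) asks for evaluable disease. This means a lesion measurable in at least one dimension, or "other lesions such as bone lesions, leptomeningeal disease, ascites, pleural/pericardial effusions, lymphangitis cutis/pulmonitis or hepatosplenomegaly from disease". For expansion (Synopsis and Section 4.2.2, item 1) the rule is "Has measurable disease as defined in Section 8.5.3".

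**Response criteria for solid tumors.** Protocol Appendix 4 (RECIST 1.1) classes most of the lesion types in the escalation list as non-measurable: "Bone lesions, leptomeningeal disease, ascites, pleural/pericardial effusions, lymphangitis cutis/pulmonitis, inflammatory breast disease". A PR there is "At least a 30% decrease in the sum of the diameters of target lesions", so it needs target lesions. The table for subjects with non-target disease only has CR, Non-CR/non-PD, Not Evaluated and PD, but no PR. Its footnote says that Non-CR/non-PD "is preferred over ‘stable disease’ for non-target disease".

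**Response criteria for CNS tumors.** Protocol Appendix 5 (RANO) states: "Subjects with non-measurable disease only cannot have a PR; the best response possible is SD". A parallel note rules out CR.

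**Analysis.** SAP 5 defines the ITT population as all dosed subjects and uses it for efficacy. SAP 15.1 plans the escalation ORR by dose level (a secondary endpoint) and the expansion ORR by cohort (primary). It then adds: "ORR will be summarized by dose level across the dose escalation and dose expansion phases and overall", with an exact 95% CI at each dose level and overall. Protocol 14.4.2 plans the same pooling ("the ORR will be summarized by dose level across the dose escalation and dose expansion parts (including cohorts) and overall"), but limits the CI to dose levels and cohorts with at least 20 subjects, plus the overall figure. The only ORR subgroup in the SAP is prior radiotherapy. Neither document has a measurable-disease set or a sensitivity analysis on measurability.

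**The concern.** Some children in the escalation denominators may be non-responders by definition, whatever the drug does. The two parts have different entry rules, and the parts do not cover the same doses. A pooled table by dose therefore mixes a difference in entry rule with a difference in dose.

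This is plausible here. Protocol 3.3 says that screening and enrollment trends in escalation pointed to a preponderance of ATRT, the group assessed by RANO, where the bar is absolute. The protocol also expressly admits leptomeningeal disease and positive CSF cytology. There is a second route as well: escalation accepts a lesion measured in one dimension, which RANO calls non-measurable.

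At stake is how the by-dose ORR will be read. Expansion doses were later split between 520 and 1200 mg/m2 BID (protocol 5.3), so readers will look across dose rows for a trend. Part of any such trend could come from eligibility alone.

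**Working it through.** **1. The plan's own figures.** Exact binomial for at least 3 responders in 20: Type I error at 5% is 0.0755 (stated 8%), and Type II error at 20% is 0.206 (stated 21%). Both reproduce. The rule is applied within expansion cohorts, so escalation subjects do not enter it. Protocol Table 1 gives 13% ORR in 85 subjects of this trial: 11/85 = 12.9%, exact 95% CI 6.6% to 22.0%, which also reproduces.

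**2. Which pooled rows are mixed.** Dose level is taken as the assigned starting dose. Escalation used 240, 300, 400, 520, 700, 900 and 1200 mg/m2 BID (protocol Table 2). Expansion suspension doses are 1200 mg/m2, and 520 mg/m2 for new non-ATRT patients under protocol 5.3. SAP 3.1 still gives 1200 mg/m2 for all of Cohorts 1 to 3, and the two passages need reconciling. So 240, 300, 400, 700 and 900 are filled from escalation only, 1200 is mixed, and 520 is mixed under the protocol.

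**3. Expected ORR at an escalation-only level.** Let q be the share with only non-measurable disease, p the true ORR in measurable disease, and c the CR rate in the non-measurable-only group (0 under RANO). Expected ORR = (1 − q)p + qc. The documents do not give q; 10% to 40% is an assumed range. The value p = 20% is the rate that the plan calls of clinical interest.

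| q | p = 20%, c = 0 | p = 20%, c = 5% (assumed, RECIST) | Shortfall at p = 13%, c = 0 |
|---|---|---|---|
| 0 | 20% | 20% | 0 |
| 10% | 18% | 18.5% | 1.3 points |
| 25% | 15% | 16.25% | 3.3 points |
| 40% | 12% | 14% | 5.2 points |

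The last column is 13% × q. The 13% is itself an all-treated figure, so it is already diluted if q is above zero.

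**4. A mixed level for comparison.** Take 1200 mg/m2 with 6 escalation children and, by assumption, 40 expansion children, with c = 0 and every expansion child measurable. Expected ORR = [6(1 − q)(0.20) + 40(0.20)]/46, which is 19.7%, 19.3% and 19.0% for q = 10%, 25% and 40%. The apparent gap to an escalation-only level is then 1.7, 4.3 and 7.0 points with no true dose effect. With 20 or 60 expansion children instead of 40, the gap at q = 25% is 3.8 or 4.5 points.

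**5. Whole-study ORR.** Use 48 planned escalation subjects and 64 in expansion (three cohorts of 20 plus the 4 in Cohort 4). Then 0.20 × [48(1 − q) + 64]/112 = 19.1%, 17.9% and 16.6% for the same q.

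**6. Against chance.** At a level of 6 children, P(no responder) = [1 − 0.20(1 − q)]^6. This is 0.26 at q = 0, and 0.30, 0.38 and 0.46 at q = 10%, 25% and 40%. The exact 95% CI for 0/6 runs from 0 to 45.9%, so at any single level chance error is larger than this bias.

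**The case against.** The strongest case against the point is that nothing decisive rests on the pooled table. Escalation tests no hypothesis, and protocol 14.1.1 calls most of its analyses descriptive or exploratory. A reader might infer that the choice of RP2D was distorted. The documents do not support that: protocol 1.5.2.2 records that the committee chose it in July 2017 on safety, PK and PD data. This stands, and it limits the point to interpretation of a descriptive result.

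Three further readings are tempting and fail:

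- **That the pooled table is the only planned look at ORR by dose.** SAP 15.1 also plans the escalation ORR by dose level, where all levels share one entry rule. That table has no confounding between parts, although its denominators also include children who cannot respond. Protocol 14.7 allows exploratory exposure-response work too.
- **That such children sit only in escalation.** Protocol 8.5.3 accepts a 10 mm lesion in one dimension and bone lesions measured by MRI. RANO needs two perpendicular diameters of at least 10 mm, and Appendix 4 lists bone lesions as non-measurable. Some expansion subjects may therefore be non-measurable under the criteria applied to them, which would narrow the gap.
- **That low-dose ORR is biased down.** The escalation-only levels include 700 and 900 mg/m2, above the 520 level. The divide is between the parts, not between low and high dose.

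It can also be said that SAP 11 already summarizes the presence of target lesions at baseline under both criteria, so a careful reader could find the share. That is partly right, but nothing links it to the ORR. Finally, making a measurable-disease subset the lead figure would depart from the protocol's ITT rule in an open-label trial with responses already tabulated, and would drop RECIST subjects who could have a CR. That objection is sound, and the fix keeps ITT in front.

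**Conclusion.** The point holds as a cheap improvement, not as a flaw in the primary analysis. The entry rules differ, the response criteria exclude some admitted children from PR or from any response, and SAP 15.1 counts them all with no supporting line. The bias is downward, unless the CR rate in RECIST non-target-only children reached the ORR in measurable disease.

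Its size cannot be known from the documents. It is zero if no such child enrolled. If q is 10% to 40%, it is 2 to 8 points at an escalation-only level with true ORR 20% and RANO assessment, or about 1 to 5 points with 13%. A reader might extend this to the expansion ORR by cohort or to the 3-of-20 rule; neither uses escalation subjects, so neither changes on this account.

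**What to change.** In SAP 15.1:

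- Keep the ITT ORR as the lead figure throughout.
- For the escalation ORR, the pooled ORR by dose level and the whole-study ORR, add a second line restricted to subjects with measurable disease at baseline under the criteria applied to them (RECIST 1.1 or RANO). Use the target-lesion indicator that SAP 11 already derives, not the Section 8.5.3 eligibility definition.
- Report the number of non-measurable-only subjects at each dose level. This count alone shows whether the problem exists.
- Show escalation and expansion separately within the 520 and 1200 mg/m2 rows.
- Add a Non-CR/Non-PD category to the best overall response table, so that RECIST subjects without target lesions have a valid row. This is a table-shell point and does not change the ORR.

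The cost is SAP wording and a few table lines from data already collected. The added line has smaller denominators and wider CIs. It does not remove the confounding of dose by tumor type, since starting doses for new patients depend on ATRT status and CNS involvement (protocol 5.3).
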